A strategy of dose titration for each treatment will be employed to bring as many participants as possible below the threshold of sUA < 6.0 mg/dl, established by guidelines and recommendations (7). The Phase 1 titration is intended to bring sUA < 6.0 mg/dl within 24 weeks. All participants will be analyzed during Phase 3 regardless of whether their sUA is < 6.0 or \geq 6.0 mg/dl. We expect that roughly equal numbers of participants in each study arm will reach this threshold. We expect that 75% - 80% participants will have a mean sUA < 6.0 mg/dl across the last 3 study visits occurring during Phase 2 at 36, 42, and 48 weeks. For secondary analysis, we define the binary outcome, mean sUA < 6.0 mg/dl as a treatment success and mean sUA \geq 6.0 mg/dl, as a treatment failure.

Choice of a Bound, B, for the Non-inferiority Test

Non-inferiority tests require expert choice of a bound, B, larger than the true difference, D, between the treatment proportions of participants with flare events (the proportion for febuxostat minus the proportion for allopurinol). The bound marks where clinicians might begin to doubt that the difference, D, is very small and close to zero. Seven rheumatologists on our Planning Committee, selected for their expertise in gouty arthritis and clinical trial design, chose B = 8%.

The null hypothesis will be rejected if U, the upper limit on the one-sided 95% confidence interval on the difference between the two flare-event rates (D), is less than B = 8%. (See Figure 1) If U exceeds B then this indicates that the true difference may be large and that allopurinol is inferior to febuxostat. (See Figure 2)

It is important to note that our choice of a bound is more conservative when compared to many other recent studies. Previous studies have chosen the true bound to be 10% and a true difference in the proportions to be 0% (11). For the non-inferiority test, this more conservative estimate requires CSP 594 to enroll a larger sample size.

Primary Data Analysis Plan

The primary hypothesis to be tested is that allopurinol is non-inferior to febuxostat. The primary outcome is the difference (D) in proportion of patients with one or more gout flares during Phase 3. The proposed test is a one-sided non-inferiority test of the null hypothesis that $U > B$, which the upper limit on the 95% confidence interval on the difference between two proportions exceeds 8%. We posit a true difference in proportions of 0%.

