The results for the primary hypothesis will be analyzed by means of a one-sided 95% confidence interval on the difference in proportion of participants with one or more gout flare events. The test of the difference between proportions will have one-sided type I error of 5%. Starting with a total of 950 participants, allowing 5% dropout, and retaining 900 participants, the test has 90% power to reject the null hypothesis of inferiority with a total of 900 participants, 450 participants per arm,

For large samples, regarding the difference between proportions as the difference between means, the use of the standard Student's t distribution closely approximates the non-central t-distribution and justifies use of the power formula 3.2.4 (in section 3.2.2) below (Chow, Shao, and Wang (86):

$$n = n_1 = n_2 = \frac{(Z_\alpha + Z_\beta)^2 2\sigma^2}{(D - B)^2}$$

Note: $n = 450$ is the number of participants in each of the two study arms, $Z_\alpha = 1.645$ is the cut point for a one-sided test with a 5%, Type I error, $Z_\beta = 1.28$ provides 90% power, Bound = 8%, $D=0\%$ is the true difference between the treatment outcome measures, and $\sigma^2 = 0.16$ is the variance associated with the distribution of for a single Bernoulli observation.

As rates are uncertain, we note that if the Phase 3 rate of gout flares is either 15%, 20%, or 25% then the respective statistical powers are 96%, 91%, and 87%. With a rate of 20%, but a higher dropout rate of 10%, the power is 90%. Non-adherence to treatment, inability to attain $sUA < 6$ mg/dl, or failure to appear for clinic visits will not affect dropout, only the explicit decision of the patient to leave the study. Participants who experience toxicity that either reduced dosage or other medications reduce to a tolerable level can remain on study if they wish to do so.

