The test of the primary hypothesis compares the treatments without adjustment for any covariates. The secondary analyses, particularly secondary analysis will confirm or not confirm the primary hypothesis by considering variations on the primary analysis including logistic regression models that adjust for covariates. We note that logistic regression analysis yields a treatment odds ratio rather than the difference between proportions. In this case, to carry out the non-inferiority test, we will estimate the difference between treatments by linking the odds ratio to the overall proportion of participants who have one or more gout flares.

In addition to testing the primary hypothesis, extensive descriptive analyses outlined in (BRDP) will compare treatments with respect to selected variables among the demographic, medical history, laboratory values, anthropomorphic, vital sign, quality-of-life, alternative outcome, and side effect variables. Simple unadjusted comparisons will apply Student's t-test to continuous variables, the Wilcoxon test to highly skewed continuous or ordinal variables and will apply the Chi-square test (or Fisher's exact test) to categorical variables.

Non-adherence

Of relevance to this study, observational studies have indicated relatively poor adherence in patients with gout (40, 87-90) However, Dalbeth et al. (91) found that higher doses of allopurinol were associated with sUA levels at target independent of adherence with treatment. Because all study participants will receive active therapies of proven efficacy for lowering sUA levels as well as prophylactic treatment of acute gout symptoms, compliance issues are expected to be minimal in this trial. Other studies in rheumatoid arthritis have shown that if patients are doing well, issues of poor treatment adherence are minimized (92).

Participant adherence to protocol-directed study treatment will be assessed via pill counts, prescription renewals, and participant interview. We will use the question and pill count data to determine if a participant took 80% or more of treatment medication. The per-protocol population will be defined as participants remaining on the same treatment throughout the entirety of the study with 80% adherence.

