Gout flares are nearly ubiquitous with initiation of effective ULT. Bias could occur if one treatment group has more gout flares than the other leading to a differential change in treatment recommendations or adherence. Indeed, these expected flares are one of the major reasons why patients and clinicians fail to continue effective therapies or to use them at appropriate doses. In order to assure protocol compliance and to avoid early withdrawal, participants will be provided with appropriate anti-inflammatory gout prophylaxis. Anti-inflammatory prophylaxis will conform to recently published guidelines in gout management (61).

XIII. Feasibility of Recruitment

We propose to enroll 950 participants from 20 VA sites. Based on national data from 2009 to 2012, Table 6 below shows the 40 VA sites with the largest estimated number of 12-month prevalent gout patients. The 12-month prevalence is the number of patients on a particular day plus the number of new patients expected within 12 months. The national data indicate that the point prevalence pool increased by about 20% during the last year. The mean pool size among the top 40 VA sites is 398. Data from VISN#1 indicate that about 50% of these patients have a sUA level > 6.8 mg/dl, and thus would be eligible. Hence, these sites need to enroll 25% of the eligible patients.

Table 6: VA sites with largest estimated number of 12-month prevalent gout patients without AKI

Site	Number of Patients	Site	Number of Patients
Buffalo, NY	786	Denver, CO	344
Kansas City, MO	657	Charleston, SC	341
St. Louis, MO	586	Boston, MA	334
Minneapolis, MN	556	Portland, OR	334
Atlanta, GA	555	Orlando, FL	330
Gainesville, FL	549	Indianapolis, IN	322
Nebraska-Western Iowa, NE	525	Loma Linda, CA	321
Tampa, FL	492	Puget Sound HCS, WA	316
Columbia, SC	490	Philadelphia, PA	311
Cleveland, OH	488	Connecticut HCS, CT	310
Richmond, VA	485	Durham, NC	309
Greater Los Angeles, CA	441	N. California HCS, CA	307
Dallas, TX	426	Albuquerque, NM	304
Milwaukee, WI	397	Washington, DC	304
Bay Pines, FL	393	Chicago HCS, IL	302
Pittsburgh, PA	386	Hines, IL	302
Mid Tennessee HCS, TN	378	Memphis, TN	298
Baltimore, MD	373	Birmingham, AL	295
Southern Arizona HCS, AZ	359	Central Texas HCS, TX	293
Houston, TX	252	Salt Lake City, UT	290

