### **3.4. Definition of per-Protocol sample**

Participant adherence to protocol-directed study treatment will be assessed via dosage review and participant interview. We will use the question and pill count data to determine if a participant took 80% or more of treatment medication. The per-protocol population will be defined as participants remaining on the same treatment in phase 3 of the study with 80% adherence.

We will compare the primary results with the analogous results for the per-protocol participants.

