## **4. Sample Size and Power**

The results for the primary hypothesis will be analyzed by using a one-sided 95% confidence interval on the difference in proportion of participants with one or more gout flare events during phase 3. The test of the difference between proportions will have one-sided type I error of 5%.

Starting with a total of 950 participants and allowing up to 10% dropout, the test has 90% power to reject the null hypothesis of inferiority with a total of 850 participants, 425 participants per treatment arm.

Sample recruitment and subsequent event rates will be summarized and presented to the DMC bi-annually. These reports will be used for monitoring the progress of the study and any modification to the recruitment schedule or the statistical analysis plan will be at the recommendation of the DMC.

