#### 5.4.1. Sensitivity Analysis

- (1) The primary analysis will be repeated on the "per-Protocol" sample with adherence as defined in 3.4 to evaluate efficacy among those adherent to the protocol. We will compare the primary results with the analogous results for the per-protocol participants.
- (2) On the "Primary Analysis" cohort assuming all allopurinol patients with missing primary outcome had at least one gout flare during phase 3 of our study while none of febuxostat patients with missing primary outcome had any gout flare during phase 3 (the worst-case scenario).
- (3) On the "Primary Analysis" cohort assuming all febuxostat patients with missing primary outcome had at least one gout flare during phase 3 of our study while none of allopurinol

patients with missing primary outcome had any gout flare during phase 3 (the best case scenario).

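### The per-protocol set counts adherence and staying on treatment after the first Phase 3 flare, so membership can depend on the outcome and the check can be biased

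*SAP*

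**What the plan says.** SAP 3.4 defines the set thus: "The per-protocol population will be defined as participants remaining on the same treatment in phase 3 of the study with 80% adherence". Protocol VIII (Non-adherence) applies the same test to a longer period: "The per-protocol population will be defined as participants remaining on the same treatment throughout the entirety of the study with 80% adherence". The primary outcome in both documents is at least one gout flare in Phase 3, weeks 49 to 72. Neither definition ends the assessment at the first flare, and nothing elsewhere keeps in the set a participant who flares and then stops.

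SAP 5.4.1 lists the per-protocol repeat first among the sensitivity analyses; its purpose is "to evaluate efficacy among those adherent to the protocol". The primary analysis (SAP 5.4) takes everyone still on study when Phase 3 begins and sets no condition on Phase 3 adherence.

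On behaviour after a flare, Protocol XII says: "Indeed, these expected flares are one of the major reasons why patients and clinicians fail to continue effective therapies". It adds that unequal flares between arms could lead to unequal adherence. That paragraph is about flares when urate-lowering therapy is started.

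**The concern.** A per-protocol set is meant to show what happens in people who took the drug as assigned. Here, membership is partly decided after the outcome has occurred. Someone who flares in week 52 and stops has taken 4 of 24 Phase 3 weeks (17%), or about 4 of 12 supplied weeks (33%, assuming a 12-week supply at week 48). Either way that person fails 80% and leaves the set, and the flare goes too. A flare-free participant can leave for other reasons but not because of a flare.

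The analysis then describes flares among people who kept taking drug after any flare. In a non-inferiority trial the adherent-population repeat is read as a test of whether poor adherence has hidden a real difference. If the rule itself removes events, agreement with the primary result is weaker evidence than it appears.

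**Working it through.** **Inputs.** One-sided alpha (SAP 4): "The test of the difference between proportions will have one-sided type I error of 5" percent. Margin (Protocol VIII): the planning rheumatologists, "selected for their expertise in gouty arthritis and clinical trial design, chose B = 8" percentage points. Febuxostat Phase 3 flare rate 20%, true difference 0 (Protocol VIII). Size: SAP 4 says "the test has 90% power to reject the null hypothesis of inferiority with a total of 850 participants, 425 participants per treatment arm"; Protocol VIII says "the test has 90% power to reject the null hypothesis of inferiority with a total of 900 participants, 450 participants per arm". D is the allopurinol minus the febuxostat flare proportion. The share of flarers removed, r, is not in the documents; the values below are assumptions.

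**Reproducing the plan.** The protocol's formula gives n = (1.645 + 1.28)² × 2 × 0.16 / 0.08² = 427.8 per arm. Power is Φ(0.08/SE − 1.645) with SE = √(2 × 0.16/n): 91.2% at 450 per arm and 89.8% at 425. The planned figures hold up.

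**Effect of the rule.** If a share r of an arm's flarers and a share s of its non-flarers are removed, the arm's flare proportion becomes p(1 − r) / [p(1 − r) + (1 − p)(1 − s)]. The chance of declaring non-inferiority is Φ((0.08 − D)/SE − 1.645), with the unpooled SE and the reduced arm sizes. True rates are set at the margin, 28% against 20%.

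Worked case, r = 20% in both arms, s = 0:
- Allopurinol: 0.28 × 0.8 / (1 − 0.28 × 0.2) = 0.224/0.944 = 23.7%, n = 425.
- Febuxostat: 0.20 × 0.8 / (1 − 0.20 × 0.2) = 0.160/0.960 = 16.7%, n = 432.
- D = 7.1 points; chance of declaring non-inferiority 9.6%.

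| Removed: allopurinol flarers / febuxostat flarers / non-flarers | D (points) | Declares non-inferiority |
|---|---|---|
| 0 / 0 / 0 | 8.0 | 5.0% |
| 10% / 10% / 0 | 7.6 | 6.9% |
| 20% / 20% / 0 | 7.1 | 9.6% |
| 30% / 30% / 0 | 6.5 | 14.0% |
| 50% / 50% / 0 | 5.2 | 31.4% |
| 30% / 30% / 10% | 6.9 | 10.1% |
| 10% / 10% / 10% | 8.0 | 5.0% |
| 30% / 10% / 0 | 3.0 | 56.8% |
| 10% / 20% / 0 | 9.3 | 1.8% |

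Starting from 425 per arm changes little: 6.8%, 9.5% and 13.6% for equal removal of 10%, 20% and 30%.

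**Where the direction turns.** With 20% of allopurinol flarers removed, D returns to 8.0 points when 25.3% of febuxostat flarers are removed, a ratio of about 1.27. If the true rates are equal at 20%, equal removal leaves D at 0; at r = 20% it only raises the chance of declaring non-inferiority from 91.2% to 93.4%.

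**The case against.** A reader might infer that the check is biased toward non-inferiority as a matter of course. The documents do not support that. They give no Phase 3 stopping rate by flare status or by arm, and the table shows shrinkage, no effect or reversal depending on who stops. Under the planning assumption of equal flare rates, equal stopping leaves D at zero.

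The behavioural evidence is also indirect. Protocol XII speaks of flares at initiation, whereas Phase 3 begins after 48 weeks of treatment. SAP 3.3 expects nearly everyone left by then to find the regimen easy, and Protocol VIII expects few compliance problems. These are expectations rather than rules, and Protocol VIII separates non-adherence from dropout, so low dropout does not settle the matter.

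Not every stopper is removed. 80% of 24 weeks is 19.2 weeks, so stopping after about week 67 still passes. If the denominator is drug supplied (the formula under SAP Table B7), stopping between about week 57.6 and week 60 without taking the second supply can also pass, at 9.6 of 12 weeks. Such people leave only if stopping breaches the requirement to remain on the same treatment, which is undefined. This makes large values of r less plausible but does not remove the dependence on the outcome.

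A reader might also infer that the trial's false-positive rate rises. It does not: the chance that the primary and per-protocol analyses both wrongly show non-inferiority cannot exceed the primary's 5%.

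Other checks exist: an ITT re-analysis (SAP 3.3), worst- and best-case runs for missing outcomes (SAP 5.4.1), and a GEE model with time-dependent adherence (Protocol VIII). Of these, only the GEE model addresses adherence, and SAP 5.5 item 8 does not name adherence among its time-dependent variables.

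**Conclusion.** The point holds in conditional form. As written, per-protocol membership can depend on what participants do after the primary event, and neither document corrects for this. When flarers are removed more often than non-flarers, at similar rates in both arms, and allopurinol is truly worse, the check leans toward non-inferiority. For assumed excess removal of 10% to 30% of flarers the loss is 0.4 to 1.5 points of an 8-point deficit, and the per-protocol test on its own passes about 7% to 14% of the time instead of 5%. Other stopping patterns give no bias or the opposite bias. Only a sensitivity analysis is affected, but it is the first one listed, and it is the SAP's named check on adherence. The change is worth making because it is cheap and because the direction of the bias could not be known from the per-protocol result itself.

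**What to change.** In SAP 3.4, define the set as participants who remain on assigned treatment with at least 80% adherence up to the first Phase 3 flare or week 72, whichever comes first. State that stopping or missing doses after the first flare excludes nobody. Use the 4-weekly patient-reported adherence and the pill counts at weeks 48, 60 and 72, counting for a flarer only records that close before the flare. For flares too early to have a Phase 3 record, use the week 36 and week 48 counts. All of these are already in the protocol's Table 5. Reconcile the period with Protocol VIII, which uses the whole study, and report the current definition beside the new one as a labelled supplementary table.

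Under this rule flare-driven stopping removes nobody, so in the margin scenario D stays at 8.0 points and the pass rate at 5.0%.

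The cost is SAP wording and some programming; no new data are needed. The downsides should be stated. Flarers are judged over a shorter window with more reliance on self-report, and non-flarers have longer to fail. As an illustration, assume 15% of non-flarers fail over the full window and half that share, 7.5%, of flarers. The rates become 0.28 × 0.925 / (0.28 × 0.925 + 0.72 × 0.85) = 29.7% and 0.20 × 0.925 / (0.20 × 0.925 + 0.80 × 0.85) = 21.4%, so D is 8.35 points, a small shift against non-inferiority.

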### **3.5. Description of the Efficacy Endpoints**

#### **3.5.1. Primary outcomes**

The primary outcome will be the proportion of participants who have at least one gout flare in the allopurinol group compared with the febuxostat group during Phase 3.

##### **Gout flares**

Prior randomized trials have used varying definitions of gout flares. In this study, the occurrence of gout flares will be documented according to recently published criteria; this approach is consistent with the approach used in gout RCTs. Subjects will be asked to keep a diary of flares. Information about the occurrence of flares will be reviewed at all ULT clinic visits and telephone encounters occurring at monthly intervals in Phase 3 with the aid of these diaries to avoid recall bias that could affect this measurement if longer intervals were used. A gout flare questionnaire will be used during each visit (Phase 1 and 2) and each call (Phase 3) to capture information on: 1) the presence of a 'warm' joint; 2) the presence of a swollen joint; 3) a corresponding pain at rest score > 3 (0 to 10 scale); 4) patient-reported gout flare; and 5) medications used to treat flares, if any. Participants will be considered to have an acute gout flare if 3 of the first 4 criteria are satisfied. This method has been demonstrated to have a sensitivity of 91% and a specificity of 82%. In addition to examining the proportion of patients with at least one flare, we will also examine the number of one-month intervals during Phase 3 with gout flares requiring treatment. Treatment of gout flares will be done at the discretion of the site investigator with guidelines provided within the protocol (See Section X. Treatment Regimens below). Because gout patients may treat their attack at the first symptoms of attack onset, which can abort the full presentation of an attack, a secondary flare definition will be used of patient-reported flare of typical characteristics above plus use of appropriate gout anti-inflammatory medication; this is a standard approach used in gout RCTs in which flares are an outcome of interest.

#### **3.5.2. Secondary outcomes**

The secondary outcomes will include:

- 1) The efficacy and tolerability in patients with CKD 3.
  - i. To determine whether the efficacy of allopurinol and febuxostat differ among those with Stage 3 CKD, a planned secondary endpoint will be the occurrence of gout flares during Phase 3 in this patient subset.

- ii. Tolerability of the two treatments will also be compared in this patient subset and will include comparisons of adverse events, serious adverse events, and related study withdrawal.
- 2) The proportion of patients achieving a sUA < 6.0 mg/dl during Phase 2 (mean level assessed at weeks 36, 42, and 48) across treatment groups.
  - 3) The proportion of having at least one gout flares in Phase 3 differ in those who reach a target sUA of < 6.0 mg/dl compared with those who do not by 48 weeks.
  - 4) The impact of study treatments and sUA levels on health-related quality of life.

Both the five-item EurQol (EQ-5D-3L) and Veterans RAND 12 (VR-12) will be collected from all participants at baseline, 24, 48 and 72 weeks.

- 5) The changes in tophi area by location among those with tophaceous gout across treatment groups and sUA levels.

We anticipate that ~20% of study participants will have tophi at enrollment. The sentinel tophus will be defined as the most prominent and/or most readily measured tophus found at the time of the baseline evaluation on the hands, elbows, feet, or ears (i.e., the most common sites for tophi). Change in tophi area will be examined at week 24, week 48, and week 72 as a secondary outcome among this informative subset of patients with tophaceous gout.

- 6) The impact of treatment on the flare rate over time.

To determine whether the total number of gout flares differs between the two treatment groups the total flare numbers occurring during observation (week 0 to 72) will be compared.

Recognizing that the duration of a gout flare typically extends from several days to 2-3 weeks, and that it may sometimes be difficult for patients to distinguish between two or more back-to-back flares and one persistent but fluctuating flare, a maximum of one gout flare will be counted for each one-month observation period. Thus, as an example, during Phase 3 (24 weeks) patients could experience a number of gout flares ranging from 0 to 6 flares.

- 7) The tolerability/toxicity of the two ULTs.

Toxicity data will be carefully collected throughout the 72 weeks of the study and compared across treatment arms. Toxicity data include rises in sUA levels, serum creatinine, CBC, liver function tests (LFTs), blood pressure, cardiovascular safety events of interest, hospitalization,

and reports of skin rashes.

8) The effects of baseline covariates and time-dependent covariates on the primary results.

